#### 4.6 EFFICACY ANALYSES

The efficacy analyses will be performed on the FAS. The analyses of the primary endpoint will be repeated on the PPS as sensitivity analysis (only if the PPS is different from the FAS).

If a patient is treated with a non-permitted treatment during the study period, then all efficacy variables measured after the intake of these not-allowed treatments will be censored for the efficacy analyses. Assessments of primary and secondary criteria after a forbidden treatment will be flagged in all listings.

The following treatments are not allowed during the study.

- Plasma exchange, blood products or derivatives other than the study drug.
- Immunomodulatory or immunosuppressant agents (e.g. including but not limited to cyclophosphamide, cyclosporine, interferon- $\alpha$ , interferon- $\beta$ 1a, anti-CD20, alemtuzumab, aziathioprine, etanercept, mycophenolate mofetil, methotrexate and haematopoietic stem cell transplantation).
- Oral or systemic corticosteroids if administered with an increasing dosage or introduced at a dose higher than 10 mg daily prednisolone or equivalent. Topical corticosteroids are permitted.
- Loop diuretics administered during the last 24 hours before an IVIg infusion.

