### **7.2. Concomitant Medication**

The term ‘concomitant medication’ refers to any medication that the patient receives at any time during the study, i.e. from screening to EOS visit. This includes the screening/baseline period, treatment period and follow-up as defined in the protocol. At each visit, the Investigator will ask the patient about any medication taken since the last visit. All concomitant medication must be recorded in the patient’s medical file and documented on the appropriate pages of the eCRF.

Treatments not allowed during the study are the following:

- Plasma exchange, blood products or derivatives other than the study drug.

- Immunomodulators/immunosuppressors agents (e.g. including but not limited to cyclophosphamide, cyclosporine, interferon- $\alpha$ , interferon- $\beta$ 1a, anti-CD20, alemtuzumab, aziathioprine, etanercept, mycophenolate mofetil, methotrexate and haematopoietic stem cell transplantation).
- Introduction or increasing dose of systemic corticosteroids therapy, and/or systemic corticosteroids therapy at a dose higher than 10 mg prednisolone per day, or equivalent. Topical corticosteroids are permitted.
- Loop diuretics administered during the last 24 hours before IVIg infusion planned date. In this case, the study drug infusion date will have to be postponed.

Routine pre-medication (to prevent known drug related adverse reaction) are not recommended to avoid masking potential AEs. However, patients who have routinely been receiving pre-medication with previous Ig treatments may continue to receive the same pre-medication.

Other medications which are necessary for the patient's welfare or well-being may be given at the discretion of the Investigator.

All concomitant medications must be recorded in the patient's medical records and documented on the appropriate pages of the eCRF.

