## **12.9. Efficacy Analysis**

### **12.9.1. Primary Efficacy Variable(s)**

#### ***12.9.1. 1. Description of the primary efficacy variable(s)***

The primary efficacy endpoint will be the responder rate at EOS visit.

Responders are defined as patients with either:

- No change or decrease in the adjusted INCAT disability score and without any change in CIDP treatment between baseline and EOS visit.

or

- An increase by 1 point in the adjusted INCAT disability score without requirement of any change in CIDP treatment between baseline and EOS visit.

If a patient is treated with a not-allowed treatment during the study period, then all efficacy variables measured after the intake of these not-allowed treatments will be censored for the efficacy analyses.

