### 3.5 DEFINITION OF THE PROTOCOL DEVIATIONS AND POPULATIONS

#### 3.5.1 Populations

The definition of analysis sets is as follows:

- Total Treated Set (TTS): all patients who received at least one administration of the study drug.
- Full Analysis Set (FAS): all TTS patients having an available assessment of the primary efficacy criterion.
- Per Protocol Set (PPS): all FAS patients without any major deviations from protocol.

If a patient is treated with a non-permitted treatment during the study period, specifically those that confound efficacy evaluation, then all efficacy variables measured after the intake of these not-allowed treatments will be censored for the efficacy analyses. Censoring of measurements will be done up to a reasonable window from the start time of a prohibited treatment where the window is determined according to the half-life of the not- allowed treatment. The window will be adjudicated prior to database lock.

The TTS will be used for the analysis of safety data.

The FAS will be used for the primary analysis of efficacy data and the PPS to test its robustness.

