#### 4.6.1 Primary Efficacy Endpoint

The primary efficacy criterion is *response* of the patients at EOS visit. A patient is defined as having a *response* (or being a *responder*) both conditions below are fulfilled.

- The patient's adjusted INCAT disability score did not increase by more than 1 between baseline and EOS visit.
- The patient's CIDP treatment was not changed between baseline and EOS visit.

A change in CIDP treatment is defined by any of the following conditions:

- Increase/decrease of the dose (g/kg) of the study treatment by 5%
- Decrease of the time between courses
- Addition of corticosteroids (equivalent of more than 10 mg/day of prednisone for more than 10 days) or immunosuppressive drugs. As this condition is not possible to derive by programming, the study physician will review all treatments with corticosteroids and immunosuppressive drugs prior to database lock and flag those who fulfil the condition
- Premature discontinuation of study drug due to insufficient response to IMP and start of other CIDP treatments such as IVIg (other than study drug), corticosteroids, immunosuppressive drugs or plasma exchange

The primary analysis of the primary efficacy criterion will be done using the baseline and last available assessment of the adjusted INCAT disability score after the first study drug administration. That is, if the score at EOS visit is missing, then the Last Observation Carried Forward (LOCF) approach will be applied and the last available adjusted INCAT disability score will replace the missing value at EOS visit.

Similarly, if the assessment of the adjusted INCAT disability score is censored due to an intake of a forbidden treatment, the adjusted INCAT disability score from the last assessment before the intake of the forbidden treatment is used as replacement for the assessment of the EOS visit.

The number and percentage of Responders at EOS will be presented with descriptive statistics. The associated exact 95% Clopper-Pearson confidence interval (CI) will be calculated for the proportion of Responders.

The primary analysis will be performed using the FAS and a sensitivity analysis will be performed using the PPS.

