##### 2) Time to relapse

Relapse is defined as as one of the following conditions:

- Adjusted INCAT disability score increase by 1 point compared to baseline

AND

Judging on the clinical examination and/or the neurological scales assessments, the Investigator considers change in patient's treatment is mandatory: increase in IVIg dosage, increase or initiation of a corticotherapy, immunosuppressive therapy, plasma exchange.

- Adjusted INCAT disability score increase by at least 2 points compared to baseline.

Time to relapse (measured from the first IMP infusion in I10E-1306) will be analysed using a Kaplan-Meier (KM) method. Patients without relapse will be considered censored at their last assessment of the INCAT disability score. Patients with a forbidden treatment intake before a relapse will be considered censored at the date of the first intake of a forbidden treatment.

KM estimates of the mean, the median as well as for the first and third quartile will be provided together with their associated 95% confidence interval. A KM-plot will be provided showing the incidence of relapse over time. Time of censoring will be displayed in the graph. A table will be included below the graph showing the number of patients "at risk" (i.e. without relapse), the number of patients with a relapse and the number of censored patients at the time points 0, 12, 24, 36 and 48 weeks.

Descriptive statistics will be provided for the time to relapse on the subset of patients with relapse until EOS.

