#### 4) Rasch-built Overall Disability Scale (R-ODS)

R-ODS will be presented with descriptive statistics at baseline, week 24 and EOS visit. The change from baseline in R-ODS will be analysed at 24 weeks and at the EOS visit.

For the endpoints 1), 3), and 4) the Hodges-Lehmann estimator and the associated 95% confidence interval will be calculated for all at-visit values as well as for the change from baseline. The change from baseline for these endpoints will be tested using a Wilcoxon signed-rank test. All statistical tests will be descriptive and will use a two-sided significance level of  $\alpha=5\%$ .

Results for response rate at 24 weeks, MRC 12 muscles sum score, Rasch-modified MRC sum score, Percentage of patients without change in CIDP treatment from baseline to 24 weeks and EOS visit, and patient and investigator CGI will be presented in listings..

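### SAP 4.6 restates the Protocol 7.2 corticosteroid ban too narrowly, so a stable new start at 10 mg/day or less is neither flagged nor censored, and SAP 4.10 does not declare the change

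*SAP*

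**What the plan says.** Protocol 7.2 lists among treatments not allowed during the study: "Introduction or increasing dose of systemic corticosteroids therapy, and/or systemic corticosteroids therapy at a dose higher than 10 mg prednisolone per day". Introduction, increase and a dose above 10 mg/day are separate grounds, and the 10 mg limit does not qualify introduction. Protocol 7.1, on prior medication, separates the same grounds.

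Protocol 12.9.1.1 attaches a consequence: "If a patient is treated with a not-allowed treatment during the study period, then all efficacy variables measured after the intake" is censored. Protocol 12.9.2.2, on the secondary variables, names only the adjusted INCAT scores for this censoring.

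SAP 4.6 keeps censoring for all efficacy variables and adds flagging in the listings, but its corticosteroid entry reads: "Oral or systemic corticosteroids if administered with an increasing dosage or introduced at a dose higher than 10 mg daily prednisolone or equivalent".

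Two further SAP rules use the same list:
- **Primary endpoint (SAP 4.6.1).** When the end-of-study (EOS) INCAT is censored, "the adjusted INCAT disability score from the last assessment before the intake of the forbidden treatment is used as replacement".
- **Time to relapse (SAP 4.6.2).** "Patients with a forbidden treatment intake before a relapse will be considered censored at the date of the first intake of a forbidden treatment".

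SAP 4.6.1 separately counts as a change in CIDP treatment: "Addition of corticosteroids (equivalent of more than 10 mg/day of prednisone for more than 10 days) or immunosuppressive drugs". SAP 4.10 lists the changes to the planned analysis and says nothing about corticosteroids or forbidden treatments.

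**The concern.** Protocol 1.1.2 names oral corticosteroids as one of three treatments with proven efficacy in CIDP, and this study is meant to describe what 0.5 g/kg I10E does as maintenance. Under the SAP list, a patient who starts a low, stable steroid dose and stays on study contributes later INCAT, grip strength and R-ODS values, and later time at risk of relapse, as if on I10E alone. The treatment-change rule in SAP 4.6.1 does not catch the start either, because its threshold is above 10 mg/day.

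The SAP list is the one that will be programmed, even if the narrowing is only a drafting slip. A slip is plausible: the entry resembles the Protocol 7.1 wording with two words dropped.

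**Working it through.** The plan gives no figure tied to this rule, so there is nothing to reproduce. The check compares the texts and then works out what restoring the list would do.

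**1. The two lists side by side (prednisolone equivalent)**

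| Steroid use during the study | Protocol 7.2 | SAP 4.6 |
|---|---|---|
| New start at 10 mg/day or less, stable | forbidden | not listed |
| New start at 10 mg/day or less, later raised | forbidden | listed, through the increase |
| New start above 10 mg/day | forbidden | listed |
| Continuing stable dose above 10 mg/day | forbidden | not listed |
| Continuing stable dose of 10 mg/day or less | allowed | allowed |

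The gap is rows 1 and 4. The steps below work through row 1.

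**2. Does another rule catch row 1?**
- SAP 4.6.1, corticosteroid condition: no, the dose is too low. The study physician's review flags only courses that meet that condition.
- SAP 3.5.1: it opens "If a patient is treated with a non-permitted treatment during the study period, specifically those that confound efficacy evaluation" but names no drugs, so it does not restore the missing case.
- SAP 3.5.2: forbidden-treatment deviations are reviewed, and a major one removes the patient from the Per Protocol Set (PPS). No link to FAS censoring is stated.
- SAP 3.2 and the fourth condition of SAP 4.6.1: these catch withdrawal for lack of efficacy, and discontinuation for insufficient response with a new CIDP treatment, at any steroid dose.

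What remains is a patient with a stable low-dose start, no recorded relapse, who stays on study.

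**3. Primary responder rate if the list is restored, per affected patient**

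INCAT is scored at every visit (Protocol 10.1.1), and a rise of 2 or more is a relapse that ends study drug (Protocol 3.1.6 and 5.4). A patient with no recorded relapse therefore normally has a pre-steroid rise of at most 1. Assume the start follows at least one post-baseline score.
- EOS rise of 1 or less: responder under both lists. Change 0.
- Later rise of 2 or more: non-responder under the SAP list. Under the protocol list the pre-steroid score is carried forward, so the patient is a responder. Change +1/n: 1/15 = +6.7 points, 1/30 = +3.3 points (n from the planned 15 to 30). Change 0 where SAP 3.2 still makes the patient a non-responder.

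**4. Time to relapse (illustration)**

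Assumptions: full 48-week follow-up; relapses at weeks 6, 12, 18, 30, 36 and 42 (one each at n=15, two each at n=30, so 40%); one other patient starts a low steroid dose at week 24.

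Protocol list, patient censored at week 24:
- n=15: 1 − (12/15)(8/11) = 41.8%
- n=30: 1 − (24/30)(17/23) = 40.9%

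SAP list, patient not censored:
- no later relapse: 1 − 9/15 = 1 − 18/30 = 40.0%
- relapse at week 39: 1 − 8/15 = 46.7%; 1 − 17/30 = 43.3%

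Restoring the list raises the 48-week estimate by 1.8 points (n=15) or 0.9 (n=30) if the patient stays relapse-free. It lowers it by 4.9 or 2.4 points if the patient later relapses. The sign depends on the patient's course.

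**5. Secondary scores**

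For R-ODS, "The change from baseline in R-ODS will be analysed at 24 weeks and at the EOS visit"; grip strength follows the same schedule. If a start before Visit 9 is censored, no post-baseline value is left. SAP 3.2 applies last observation carried forward to secondary endpoints without saying whether baseline may be carried. If it may, the change is forced to zero.

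**The case against.** The strongest reply is that the clinically important patients are already handled. A 1-point INCAT rise where the investigator judges starting a steroid mandatory is a relapse at any dose (Protocol 3.1.6, SAP 4.6.2). Relapse requires discontinuation, with EOS assessments before other CIDP treatment, and discontinuation for insufficient response makes the patient a non-responder. This stands and leaves a small residue, which would include low-dose courses for unrelated illness.

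It is also fair that the protocol is not uniform. Protocol 12.9.2.2 names only adjusted INCAT for secondary censoring, so a reader should not infer that the protocol plainly requires grip strength and R-ODS to be censored. Protocol 12.9.1.1 and SAP 4.6 itself do say all efficacy variables. The rule that censors time to relapse at forbidden intake comes from the SAP.

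Deviations are listed, concomitant drugs are tabulated, the primary analysis is repeated on the PPS, and Protocol 12.2 promises that changes will be discussed in the study report. These make the patient visible, but they do not restore censoring in the FAS. The report can discuss the change only if someone has noticed it.

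The Kaplan-Meier illustration rests on assumed relapse times and full follow-up, although SAP 4.10 reports early termination. It shows scale and sign only.

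**Conclusion.** The mismatch is real and should be corrected, but it is minor. The SAP list contradicts Protocol 7.2 on two kinds of corticosteroid use, and score censoring, flagging, EOS replacement and time-to-relapse censoring all follow that list.

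A reader might infer that the narrowing inflates the responder rate. The documents do not support that. With at least one post-baseline score before the start and no recorded relapse, correcting the list moves the primary rate by 0 or up by 1/n per affected patient. A reader might also infer that steroid rescue after treatment failure is counted as response. It is not where the patient is withdrawn for insufficient response.

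The effect falls mainly on the secondary scores and the relapse curve, and its direction is not established. The number of affected patients is not given and may be zero.

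**What to change.** Replace the corticosteroid entry in SAP 4.6 with the Protocol 7.2 wording: introduction, increase, and/or any dose above 10 mg/day prednisolone equivalent. Topical use stays permitted.

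Add two safeguards, because wider censoring has side effects:
- List any worsening or relapse that occurs after such a start, so that censoring does not hide it.
- For grip strength and R-ODS, report a value as missing when censoring leaves no earlier post-baseline value, rather than carrying baseline forward.

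Optional: a sensitivity responder rate that counts any steroid initiation for CIDP as non-response. It would lower the rate by 1/n per reclassified responder, but it answers a different question and does not measure this defect. It would need the indication recorded, so that courses for unrelated illness are not misclassified. A sentence in SAP 4.10 stating the SAP 4.6.1 steroid threshold would be documentation only.

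The cost is one corrected line, one sentence on missing values and one short listing, all before database lock. The study physician already reviews every corticosteroid treatment at that stage.

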#### 4.6.1 Primary Efficacy Endpoint

The primary efficacy criterion is *response* of the patients at EOS visit. A patient is defined as having a *response* (or being a *responder*) both conditions below are fulfilled.

- The patient's adjusted INCAT disability score did not increase by more than 1 between baseline and EOS visit.
- The patient's CIDP treatment was not changed between baseline and EOS visit.

A change in CIDP treatment is defined by any of the following conditions:

- Increase/decrease of the dose (g/kg) of the study treatment by 5%
- Decrease of the time between courses
- Addition of corticosteroids (equivalent of more than 10 mg/day of prednisone for more than 10 days) or immunosuppressive drugs. As this condition is not possible to derive by programming, the study physician will review all treatments with corticosteroids and immunosuppressive drugs prior to database lock and flag those who fulfil the condition
- Premature discontinuation of study drug due to insufficient response to IMP and start of other CIDP treatments such as IVIg (other than study drug), corticosteroids, immunosuppressive drugs or plasma exchange

The primary analysis of the primary efficacy criterion will be done using the baseline and last available assessment of the adjusted INCAT disability score after the first study drug administration. That is, if the score at EOS visit is missing, then the Last Observation Carried Forward (LOCF) approach will be applied and the last available adjusted INCAT disability score will replace the missing value at EOS visit.

Similarly, if the assessment of the adjusted INCAT disability score is censored due to an intake of a forbidden treatment, the adjusted INCAT disability score from the last assessment before the intake of the forbidden treatment is used as replacement for the assessment of the EOS visit.

The number and percentage of Responders at EOS will be presented with descriptive statistics. The associated exact 95% Clopper-Pearson confidence interval (CI) will be calculated for the proportion of Responders.

The primary analysis will be performed using the FAS and a sensitivity analysis will be performed using the PPS.

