#### **3.1.5. Follow-up and End of Study**

Three weeks after visit V16, patients will undergo an EOS visit. This visit corresponds to visit V17 (Week 48).

In the event of premature discontinuation of the study drug or patient withdrawal from the study, an EOS visit will be performed within 7 days and prior to administration of any other treatment for CIDP (see Section [8.2.5](#)). The reason for premature study drug discontinuation / study withdrawal should be accurately documented, as well as the planned new treatment to be administered if any.

The total duration of the study for a patient is approximately 48 weeks.

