### **3.1.6. Relapsing Patients**

A relapse is defined as one of the following conditions:

- Adjusted INCAT disability score increase by 1 point compared to baseline,  
AND  
Judging on the clinical examination and/or the neurological scales assessments, the Investigator considers change in patient's treatment is mandatory: increase in IVIg dosage, increase or initiation of a corticotherapy, immunosuppressive therapy, plasma exchange.
- Adjusted INCAT disability score increase by at least 2 points compared to baseline.

Relapsing patients will undergo the study assessments scheduled at the EOS visit within 7 days and prior to the administration of any other CIDP treatment. The patient will be then withdrawn from the study and treated at the discretion of his/her physician.

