## **3.2. Endpoints**

### **3.2.1. Primary Efficacy Endpoint:**

The primary efficacy endpoint will be the responder rate at EOS visit.

Responders are defined as patients with either:

- \* No change or decrease in the adjusted INCAT disability score and without any change in CIDP treatment between baseline and EOS visit.  
or
- \* An increase by 1 point in the adjusted INCAT disability score without requirement of any change in CIDP treatment between baseline and EOS visit.

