### **5.4. Discontinuation Criteria / Stopping Rule(s)**

All patients are free to withdraw from participation in this study at any time, for any reason, and without prejudice. The Investigator must withdraw from the study any patient who requests to stop participating in the study. Patients who withdraw their consent will be asked to undergo the study assessments scheduled at the EOS visit. They will be advised that participation to the EOS visit is voluntary but is their best interest.

The Investigator must discontinue study drug administration to a patient and perform an EOS visit at the request of the Sponsor or if the patient:

- Experiences an AE - including a clinically significant laboratory abnormality -that justifies study drug premature discontinuation.
- Undergoes protocol deviation that could endanger the patient safety.
- Becomes pregnant.
- Relapses.

Relapsing patients will undergo the study assessments scheduled at the EOS visit within 7 days and prior to the administration of any other CIDP treatment. The patient will be then withdrawn from the study and treated at the discretion of his/her physician.

If a patient is prematurely discontinued, the date, reason of discontinuation and any change in CIDP treatment will be documented.

If a patient is withdrawn because of an AE, he/she will be followed up until complete resolution or stabilisation of the AE.

Patients lost to follow-up will be considered as discontinued from the study. A patient will be considered as lost to follow-up only after having exhausted all means of contact. Investigators must make every effort to contact the patient and/or his/her family or relatives to obtain the maximum of the per protocol requested information. All contact attempts should be documented in the patient's medical records

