#### **8.2.5. Visit 17: Week 48 (+/- 7 days) – End of study visit**

At the end of the follow-up period, patients undergo an end of study visit evaluation. In the event of premature discontinuation from the study drug or patient withdrawal from the study, an end of study visit is performed anyway within 72 hours.

The end of study assessment should be performed before any other treatment including Igs is administered.

The reason for premature study drug discontinuation / study withdrawal should be accurately assessed and entered into the eCRF.

The following study procedure will be carried out:

- Complete physical examination.
- Vital signs: temperature, heart rate, systolic and diastolic blood pressure.
- Neurological status assessment:
  - INCAT disability score (adjusted INCAT disability score will be deduced from reported values).
  - Patient and Investigator Clinical Global Impression-Severity (CGI-S), Clinical Global Impression-Efficacy (CGI-E) and Clinical Global Impression-Improvement (CGI-I).
  - MRC sum score.
  - Rasch-modified MRC sum score.
  - R-ODS.
  - Grip strength with Martin vigorimeter in both hands.
- Biological tests in local laboratory:
  - \* Haematology:
    - Complete blood count + differentials, haemoglobin (Hb), mean corpuscular volume (MCV), platelets count.
    - Haptoglobin.
    - Reticulocytes, direct Coombs test.
  - \* Biochemistry:
    - Creatininemia, glomerular filtration rate according to MDRD.
    - LDH.
    - Total and free bilirubin (total bilirubin in all patients; if total bilirubin > ULN, free bilirubin will be assessed from the same blood sample, as total bilirubin).
    - AST, ALT, ALP,  $\gamma$ GT.
    - Total serum protein level
  - \* C3 and C4 antigens.
  - \* Total serum IgG trough levels

- \* HBs Ag, anti HBs & anti HBc antibodies, HIV, HCV tests.
  - Serum reference sample for long term storage.
- \* Urine protein reagent strip test [to be performed in patients who at screening in I10E-1302 Clinical Study tested for urine protein reagent strip result "1 cross 1 (+)" and/or had GFR in the range of 60-80 mL/min/1.73m^2]:

If urine protein reagent strip test result = Negative or Trace	Action: No further urine test required

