### **12.2. Statistical Analysis Plan**

The material of this section is the basis for the Statistical Analysis Plan (SAP) of the study.

The detailed technical aspects of the statistical analyses will be provided in the SAP. The SAP will possibly take protocol amendments into account and adapt to unexpected issues raised by the trial running and/or data that affect planned analyses in the protocol.

Any changes from the protocol will be discussed in the study report.

Prior to locking the database, a data review meeting will be planned in order to review individual data and validate the SAP.

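### For a 1-point INCAT worsening the SAP tests whether treatment was changed, not whether a change was required, so a completer first judged at V17 to need a change is both a relapse and a responder

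*SAP*

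**What the plan says.** Protocol 3.2.1 and 12.9.1.1 define response by two alternatives with different treatment conditions. For a stable or improved score the condition is "No change or decrease in the adjusted INCAT disability score and without any change in CIDP treatment between baseline and EOS visit". For a 1-point worsening it is "An increase by 1 point in the adjusted INCAT disability score without requirement of any change in CIDP treatment between baseline and EOS visit".

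SAP 2.5.1 and 4.6.1 merge the two. A responder has an increase of at most 1 point and meets the single condition "CIDP treatment was not changed between baseline and EOS visit". Change is then defined by four events: a 5% change in study dose, a shorter interval between courses, added corticosteroids or immunosuppressants, or premature discontinuation for insufficient response together with the start of another CIDP treatment. A judgement that change is needed is not among them. SAP 3.2 adds that a patient withdrawn for lack of efficacy is a non-responder.

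The relapse definition in SAP 4.6.2 keeps the judgement: a 1-point increase is a relapse when the investigator considers a treatment change mandatory. An increase of 2 points or more is a relapse in any case.

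On timing, Protocol 3.1.5 states "Three weeks after visit V16, patients will undergo an EOS visit", and V16 is the last of the 16 dosing visits. Protocol 8.2.5 adds: "The end of study assessment should be performed before any other treatment including Igs is administered". For relapsing patients, Protocol 3.1.6 likewise requires the "study assessments scheduled at the EOS visit within 7 days and prior to the administration of any other CIDP treatment".

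**The concern.** The protocol's condition for a 1-point worsening mirrors its relapse definition, so that a patient cannot both relapse in this way and respond. Replacing required change by actual change breaks that link at the last visit, because treatment prompted by the V17 judgement can only start after the EOS assessments.

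Two things are at stake. The same patient can appear as a relapse in one table and a responder in another. And the primary endpoint no longer follows the protocol definition, with no entry in SAP 4.10, although that section does list other changes. The loss of wording is not confined to one place: a secondary criterion refers to no requirement of change in SAP 2.5.2, but becomes patients without change in SAP 4.6.2.

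**Working it through.** **1. The rules side by side.** Take a patient with no actual treatment change by EOS. Cross the INCAT change (0, +1, +2) with judged need for change (no, yes) and recorded withdrawal for lack of efficacy (no, yes), which gives 12 combinations.

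| INCAT change | Change judged necessary | Withdrawn for lack of efficacy | Protocol responder | SAP responder (with 3.2) | SAP relapse |
|---|---|---|---|---|---|
| 0 | either | no | yes | yes | no |
| 0 | either | yes | yes | no | no |
| +1 | no | no | yes | yes | no |
| +1 | no | yes | yes | no | no |
| **+1** | **yes** | **no** | **no** | **yes** | **yes** |
| +1 | yes | yes | no | no | yes |
| +2 | either | either | no | no | yes |

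Only the bold row is both SAP responder and relapse. It is also the only row where the SAP counts a responder whom the protocol does not.

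**2. Who can be in that row.** Before V17, a relapsing patient comes under Protocol 5.4: "The Investigator must discontinue study drug administration to a patient and perform an EOS visit". If the reason is recorded as insufficient response, SAP 3.2 makes the patient a non-responder. A completer at V17 has already had all 16 doses, so there is no premature discontinuation for the fourth SAP event to catch. SAP 4.1 counts completers separately from patients withdrawn early, so SAP 3.2 does not by its terms reach a completer.

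**3. Effect per patient.** The plan gives no sample size calculation or target rate to reproduce, only an expected 15 to 30 patients. One patient moves the rate by 1/15 = 6.7 points or 1/30 = 3.3 points. With assumed counts and Clopper-Pearson 95% intervals:

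- n=15: 10/15 = 66.7% (38.4 to 88.2) becomes 11/15 = 73.3% (44.9 to 92.2).
- n=30: 20/30 = 66.7% (47.2 to 82.7) becomes 21/30 = 70.0% (50.6 to 85.3).

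**4. How many such patients.** The documents do not say. As an assumption, take a constant relapse hazard at the 24-week rates that Protocol 1.1.2 cites from a placebo-controlled IVIg trial: 13% on 1 g/kg and 45% on placebo. Twenty-four weeks is 8 three-week intervals, and V17 closes the 16th. With r the 24-week rate, the probability per interval is p = 1 − (1 − r)^(1/8), and the probability of first relapse at V17 is p(1 − p)^15.

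- r = 13%: p = 1 − 0.87^(1/8) = 1.73%; relapse-free to V16 = 0.87^(15/8) = 0.770; first relapse at V17 = 1.33%. Expected 0.20 of 15 or 0.40 of 30. Chance of none: 0.9867^15 = 0.82 or 0.9867^30 = 0.67.
- r = 45%: p = 1 − 0.55^(1/8) = 7.20%; relapse-free to V16 = 0.55^(15/8) = 0.326; first relapse at V17 = 2.35%. Expected 0.35 of 15 or 0.70 of 30. Chance of none: 0.9765^15 = 0.70 or 0.9765^30 = 0.49.

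The choice of rate hardly affects the top of the range: p(1 − p)^15 is largest at p = 1/16, where it is (1/16)(15/16)^15 = 2.37%, or 0.71 of 30. Under this assumption the counts are upper figures, because relapses of 2 points or more are already non-responders and early termination (SAP 4.10) leaves fewer patients at V17.

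**The case against.** **The protocol may not exclude this patient either.** Its phrase about the period from baseline to EOS could attach to the change rather than to the requirement, and a change first judged necessary at V17 happens after EOS. But since every EOS assessment precedes new treatment, that reading leaves the condition almost nothing to exclude, and gives no purpose to the different wording in the two alternatives.

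**A site might code a V17 relapse as withdrawn for insufficient response**, because Protocol 3.1.6 makes no exception for V17. SAP 3.2 would then apply and the conflict would disappear. This is possible, but the SAP does not say so for someone who has completed the study, and the primary endpoint should not depend on how a disposition field is filled in.

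**The judgement may not be captured for completers.** The V17 procedures in Protocol 8.2.5 list no such item, and the eCRF content is not in the documents. This stands as something to verify. It does not rescue the SAP definition, because without the judgement the relapse endpoint could not be derived at V17 either.

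**The effect is small and the change may be reported later.** Both are true. The study tests no primary hypothesis, the relapse stays visible in the Kaplan-Meier analysis, and Protocol 12.2 says "Any changes from the protocol will be discussed in the study report". This limits the consequence but does not make the two definitions agree.

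**Conclusion.** The concern holds. For a 1-point increase, SAP 4.6.1 departs from the protocol's primary definition, and a completer first judged at V17 to need a change is both a relapse and a responder. That rests on the wording alone.

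The size is 3.3 to 6.7 points per affected patient. The expected number, below one and quite possibly zero, rests on the constant-hazard assumption and on rates from another trial at other doses. This gap can only raise the responder rate. Other SAP conditions (the 5% dose rule, the shorter interval, SAP 3.2) can lower it, so the net direction against the protocol definition is unknown.

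The same conflict could arise at an early EOS visit after the study was terminated, but only if the stop was recorded under a reason other than insufficient response. The documents do not say how those stops were coded, so no figure is given. The point should be fixed, but it does not threaten the study's interpretation by itself.

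**What to change.** Add to SAP 2.5.1 and 4.6.1:

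> A patient with a 1-point increase at EOS, or at the assessment carried forward, is a responder only if the investigator did not judge a change in CIDP treatment to be required at or before EOS, whatever reason is recorded for stopping.

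Cross-refer there to the rule in SAP 3.2 on withdrawal for lack of efficacy, and list any remaining departure from the protocol definition in SAP 4.10. The endpoint stays response at EOS.

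The cost is one sentence, one cross-reference and at most one entry in SAP 4.10. No new data should be needed, since the relapse endpoint already relies on the same judgement; confirm that it is recorded for patients who complete V17. The responder rate may come out slightly lower.
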